7.2.2.5 Weekly Assessments

- Clinical toxicity assessment
- Concomitant medications review
- Hematology, including complete blood count with white blood cell differential
- Serum chemistry, including sodium, potassium, chloride, magnesium, CO₂, BUN, creatinine, glucose, calcium, albumin, total protein, total bilirubin, AST, ALT, alkaline phosphatase

7.2.3 Cycle 2 Day 1 ±3 Day and Onwards (Cycle 3+)

These tests should be performed prior to first dose

- Clinical toxicity assessment
- Concomitant medications review
- Physical examination: Day 1*
- Weight
- ECOG performance status (Day 1; [APPENDIX III](#))
- Vital signs
- Hematology (Day 1*), including complete blood count with white blood cell differential
- Serum chemistry (Day 1*), including sodium, potassium, chloride, magnesium, CO₂, BUN, creatinine, glucose, calcium, albumin, total protein, total bilirubin, AST, ALT, alkaline phosphatase
- ECGs: see [Table 12](#)

7.2.3.1 Cycle 2 Days 1-7

- Clinical toxicity assessment
- Concomitant medications review
- Vital signs, including blood pressure, heart rate, respiration rate and temperature, collected 2 hours into APR-246 infusion (± 30 min) and at EOI (± 30 min)
- *Only in cohorts with venetoclax.* Venetoclax administration: 400 mg (4 tablets) once daily, at approximately the same time every day, with a meal and water. If a prophylactic antifungal agent is administered concurrently, the daily dose of venetoclax should be determined based on institutional practice and current prescribing information for venetoclax. *Note:* Day 4 of Cycles 2-5 only: Blood sample for venetoclax pharmacokinetics in the presence of APR-246 ([Table 10](#))
- APR-246 administration: Days 1 – 4
- Azacitidine administration, *only in cohorts with azacitidine.* Administered daily for 7 consecutive days starting on Day 1 (Days 1 to 7 inclusive). The same route should be maintained over the 7-day treatment period. On Days 1-4 azacitidine is given immediately after APR-246 infusion
- Blood sample for APR-246 pharmacokinetics: on Day 4, per [Table 9. Samples for APR-246 to be taken 1-3 hours after completion of APR-246 administration.](#)

- ECG: standard 12-lead ECGs with patient in semi-recumbent position prior to the PK blood draw before APR-246 infusion on Day 1, per [Table 12](#)

7.2.3.2 Cycle 2 Day 8 (±3 Days)

- Clinical toxicity assessment
- Concomitant medications review
- Hematology, including complete blood count with white blood cell differential, weekly
- Serum chemistry, including sodium, potassium, chloride, magnesium, CO₂, BUN, creatinine, glucose, calcium, albumin, total protein, total bilirubin, AST, ALT, alkaline phosphatase, weekly
- *Only in cohorts with venetoclax.* Venetoclax administration: 400 mg (4 tablets) once daily, at approximately the same time every day, with a meal and water. If a prophylactic antifungal agent is administered concurrently, the daily dose of venetoclax should be determined based on institutional practice and current prescribing information for venetoclax

7.2.3.3 Cycle 2 Day 15 (±3 Days)

- Clinical toxicity assessment
- Concomitant medications review
- Hematology, including complete blood count with white blood cell differential, weekly
- Serum chemistry, including sodium, potassium, chloride, magnesium, CO₂, BUN, creatinine, glucose, calcium, albumin, total protein, total bilirubin, AST, ALT, alkaline phosphatase, weekly
- *Only in cohorts with venetoclax.* Venetoclax administration: 400 mg (4 tablets) once daily, at approximately the same time every day, with a meal and water. If a prophylactic antifungal agent is administered concurrently, the daily dose of venetoclax should be determined based on institutional practice and current prescribing information for venetoclax

7.2.3.4 Cycle 2 Day 22 (±3 Days)

- Clinical toxicity assessment
- Concomitant medications review
- Hematology, including complete blood count with white blood cell differential, weekly
- Serum chemistry, including sodium, potassium, chloride, magnesium, CO₂, BUN, creatinine, glucose, calcium, albumin, total protein, total bilirubin, AST, ALT, alkaline phosphatase, weekly
- *Only in cohorts with venetoclax.* Venetoclax administration: 400 mg (4 tablets) once daily, at approximately the same time every day, with a meal and water. If a prophylactic antifungal agent is administered concurrently, the daily dose of

venetoclax should be determined based on institutional practice and current prescribing information for venetoclax

7.2.4 End of Odd Numbered Cycles

- Response assessment, based on peripheral blood (blasts percentage)

7.2.5 End of Even Numbered Cycles

- Bone marrow sample for response assessment (blasts percentage)
- Bone marrow aspirate for exploratory objectives (if no aspirate is available, then peripheral blood is acceptable)

7.3 End of Treatment Visit

This visit should take place within 28 days of the last dose of study treatment, if treatment is stopped early for any reasons.

- Physical examination
- Weight
- Vital signs
- Disease assessment
- Bone marrow aspirate for exploratory objectives. If no aspirate is available, then peripheral blood is acceptable
- ECOG performance status ([APPENDIX III](#))
- Hematology, including complete blood count with white blood cell differential
- Serum chemistry, including sodium, potassium, chloride, magnesium, CO₂, BUN, creatinine, glucose, calcium, albumin, total protein, total bilirubin, AST, ALT, alkaline phosphatase
- Clinical toxicity assessment up to 30 days after the last dose

7.4 Long-Term Follow-Up

Long-term follow-up can be done remotely (e.g. via telephone, via local practitioner or via review of medical records). After a patient is removed or withdrawn from the study, the patient will be followed until death or withdrawal of consent for study participation. Off-treatment data on overall survival will be updated every month (i.e. every 28 days ±3 days) or until death, whichever occurs first. If a patient is removed from the study due to unacceptable AEs, the event(s) will be followed until resolution or stabilization of the AE. Patients who respond and discontinue study treatment for reasons other than PD should have response assessments and survival should be collected every month until relapse or death, whichever occurs first. After relapse, data for survival should be collected every month until death or withdrawal of consent for study participation, whichever occurs first.

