Duration of Follow-Up	
Patients will be followed as per the Study Calendar. After a patient is removed or withdrawn from study treatment, the patient will be followed until death or withdrawal of consent for study participation.
 
Off-treatment data on overall survival will be updated every month (i.e. every 28 days ±3 days) or until death or withdrawal of consent for study participation, whichever occurs first. If a patient is removed from the study due to unacceptable adverse events (AEs), the event(s) will be followed until resolution or stabilization of the adverse event. Patients who respond and discontinue study treatment for reasons other than PD should have response assessments and survival should be collected every month until relapse, death or withdrawal of consent for study participation, whichever occurs first. After relapse, data for survival should be collected every month (i.e. every 28 days ±3 days) until death or withdrawal of consent for study participation, whichever occurs first.
 
Criteria for Removal from Study Treatment
 
Study treatment can continue for patients receiving clinical benefit, unless one or more withdrawal criteria are met, or at the patient's discretion, or if the study is terminated.
 
1. Study Treatment Discontinuation
 
Study treatment must be discontinued if:
 
• Evidence of disease progression. Patients who have relapsed or progressive disease but who are continuing to derive clinical benefit in the opinion of the investigator may continue to receive study treatment.• A patient becomes pregnant.• A patient is significantly non-compliant with the requirements of the protocol.• A patient has an adverse experience that would, in the Investigator's judgment, make continued participation in the study an unacceptable risk.• The patient starts new treatment for their underlying disease. 
2. Patient Withdrawal from Study Treatment
 
If the patient is permanently withdrawn from study treatment, but does not withdraw consent from the Study, the Investigator must make every effort to have the patient complete all withdrawal assessments at the time of withdrawal and complete all scheduled follow-up visits.

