- q. Please consult Section [8.4](#) for PK collection schedule.
- r. Patients discontinuing treatment should complete their end of treatment visit within approximately 28 days of their last dose of APR-246. Physical exam, vital signs, clinical toxicity assessment, hematology, serum chemistry and bone marrow aspirate and biopsy with NGS analysis should be performed, if feasible.
- s. Long-term follow up can be done remotely (e.g. via telephone, via local practitioner or via review of medical records). Assuming there is no withdrawal of consent, patients who stop study treatment for any reason (e.g. toxicity, transition to SCT, PD) will continue long-term follow-up (see Section [7.4](#)). If a patient is removed from the study due to unacceptable AEs, the event(s) will be followed until resolution or stabilization of the AE. Off-treatment data on overall survival will be updated every month (i.e. every 28 days \pm 3 days) or until death or withdrawal of consent for study participation, whichever occurs first. If a patient is removed from the study due to unacceptable adverse events (AEs), the event(s) will be followed until resolution or stabilization of the adverse event. Patients who respond and discontinue study treatment for reasons other than PD should have response assessments and survival should be collected every month until relapse, death or withdrawal of consent for study participation, whichever occurs first. After relapse, data for

survival should be collected every month (i.e. every 28 days ± 3 days) until death or withdrawal of consent for study participation, whichever occurs first.

- t. AE description, grade and start date and resolution date should be documented.

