8.3 Progression-Free Survival (PFS)

Progression-free survival (PFS) is defined for each patient as the time from start of treatment to the date of the first documented progression or death due to any cause. Patients who die without a reported prior progression will be considered to have progressed on the date of their death. Patients who did not progress or die will be censored on the date of their last evaluable tumor assessment. Patients who started any subsequent therapy without a prior reported progression will be censored at the last evaluable tumor assessment prior to the initiation of the subsequent anticancer therapy.

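### After the end-of-treatment visit, disease assessments are scheduled only for responders, so later progression in non-responders who stop without PD is not systematically captured for PFS

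*Combined protocol and SAP*

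**What the plan says.** PFS is listed as a secondary objective (3.0, objective 5) and a secondary endpoint (9.3.2, item 7) without restriction to responders.

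The follow-up rules after treatment stops are:

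- **All patients, once.** Section 7.3 sets an end-of-treatment visit that includes a disease assessment: "This visit should take place within 28 days of the last dose of study treatment, if treatment is stopped early for any reasons". Footnote r of Table 8 adds that "bone marrow aspirate and biopsy with NGS analysis should be performed, if feasible".
- **All patients, thereafter.** Section 7.4: "Off-treatment data on overall survival will be updated every month". The contact may be remote: "Long-term follow-up can be done remotely (e.g. via telephone, via local practitioner or via review of medical records".
- **Responders only, thereafter.** Section 7.4: "Patients who respond and discontinue study treatment for reasons other than PD should have response assessments", monthly until relapse or death. The synopsis (Duration of Follow-Up) and footnote s of Table 8 use the same wording.

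Section 8.3 then fixes how PFS is dated. For deaths: "Patients who die without a reported prior progression will be considered to have progressed on the date of their death". For patients alive: "Patients who did not progress or die will be censored on the date of their last evaluable tumor assessment". Patients who start a subsequent therapy without reported progression are censored at the last evaluable assessment before it.

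**The concern.** The off-treatment rule suits duration of response. It runs to relapse, which Appendix I defines for patients with prior CR, CRi or MLFS. The PFS event for a patient with stable disease is PD, and after the end-of-treatment visit nothing scheduled looks for it.

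The affected patients are foreseeable. Treatment can end for a TEAE that has not resolved (6.2), an unacceptable risk or non-compliance (5.6.1), or at the patient's discretion (5.6). Some of these patients will have stable disease at that point.

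Whether and when a PFS event is recorded therefore depends on response status. Where death supplies the event date, the error runs in one direction. An assessment that was never made cannot be recovered at analysis.

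**Working it through.** The documents give no sample size, event count or assumed rate for PFS, so there is no plan figure to reproduce. The check is a reading of the rules, followed by an illustration of size.

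**Step 1: follow one patient through the rules.** A patient with stable disease stops for toxicity, without PD and without new therapy.

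1. The disease assessment at the end-of-treatment visit falls within 28 days of the last dose.
2. Under Appendix I, PD by blast increase needs two consecutive assessments at least 28 days apart. The visit can confirm a rise already seen, or show new extramedullary disease. A first rise found there has no scheduled confirmation in a non-responder.
3. After that, only survival is scheduled.
4. If the patient progresses and dies, 8.3 dates PFS at death. If alive at cut-off, PFS is censored at the last evaluable assessment.

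Section 9.5 and the synopsis statistics text count only death from AML, against any cause in 8.3 and 9.3.2. Under that wording a non-AML death would not be an event at all. The working below follows 8.3.

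**Step 2: size.** All inputs are assumed; none comes from the documents.

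- Time to progression is exponential with median 4 months: λ = ln 2 / 4 = 0.1733 per month.
- A share q of the cohort (10%, 20% or 30%) is set to stop at a time uniform on months 1 to 4, unrelated to prognosis. Anyone who progresses first counts as observed.
- The end-of-treatment visit covers one further month, so progression is unseen only after month 2 to 5.
- Median survival after progression is 2 to 4 months, and death supplies the PFS date.

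Chance that progression is unseen, given set to stop:
(e^(−2λ) − e^(−5λ)) / (3λ) = (0.7071 − 0.4204) / 0.5199 = 0.551.

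Mean overstatement per affected patient (median / ln 2):
2 / 0.693 = 2.9 months, to 4 / 0.693 = 5.8 months.

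True 6-month PFS: e^(−6λ) = 2^(−1.5) = 35%.

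Results from 400,000 simulated patients per setting. The denominator 33 is the full size of expansion cohorts 2 and 5 in 9.1.

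| q | Unseen progression (0.551 × q) | Of 33 | Recorded median, months | Recorded 6-month PFS |
|---|---|---|---|---|
| 0 | 0 | 0 | 4.0 | 35% |
| 10% | 5.5% | 1.8 | 4.05-4.07 | about 37% |
| 20% | 11.0% | 3.6 | 4.15-4.16 | about 38% |
| 30% | 16.5% | 5.5 | 4.21-4.23 | 39-40% |

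The recorded curve can also be integrated directly: S(t) = e^(−λt) + q ∫ w(x) λ e^(−λx) e^(−μ(t−x)) dx over 0 to t. Here w(x) is the chance that the covered period ended before x, and μ = ln 2 / (median survival after progression). This gives medians of 4.06 to 4.25 over the same range, within about 0.02 of the simulation.

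**Step 3: what q means.** Some of the share set to stop progress first. The fraction that actually stops before progressing is (e^(−λ) − e^(−4λ)) / (3λ) = (0.8409 − 0.5) / 0.5199 = 0.656. The 10-30% in the table therefore corresponds to 6.6-19.7% of the cohort actually stopping without PD. If 10-30% actually stopped, q would be 15-46% (10% and 30% divided by 0.656). The same formula then gives 2.8-8.3 of 33 with unseen progression, medians of 4.10-4.44 months and 6-month PFS of 37-42%.

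**Step 4: the censored path.** If the affected patients are censored at the end-of-treatment assessment instead, the simulated median stays at about 4.0 months, because stopping was assumed unrelated to prognosis. If it is related, the estimate is biased in a direction that depends on the relation.

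**The case against.** **The group is narrow.** ORR counts PR and MLFS as responses, so the gap is essentially stable disease. Patients who start new therapy are censored under 8.3 in any case. Section 4.4 asks for at least 6 months of treatment in patients without progression or unacceptable toxicity. All of this stands, and it limits the size.

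**Progression may still surface.** Local practitioners and record review are allowed routes, and the synopsis asks patients withdrawn from treatment to "complete all withdrawal assessments at the time of withdrawal and complete all scheduled follow-up visits". This stands in part. No scheduled follow-up visit is specified to include a disease assessment for non-responders, and nothing requires a progression date to be collected. Table 8 may carry a hematology mark under long-term follow-up, which should be checked in the source table. If it does, counts would be available, but no PD determination is called for.

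**Nothing formal depends on PFS.** It is one of nine secondary endpoints in a Phase I safety study and is summarised by Kaplan-Meier. No test, sample size or dose decision uses it. This stands. The effect is on interpretation of the curve.

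**Stronger readings that the documents do not support.**

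- A reader might infer that progression in non-responders is never observed once treatment stops. The disease assessment at the end-of-treatment visit contradicts that.
- A reader might count every early stopper as an unobservable event, for example 3-10 of 33 at 10-30%. Some will be caught at that visit, die without progressing, or start new therapy.
- A reader might infer that PFS is always lengthened. That follows only where death supplies the date.
- The 7.9-month median OS in 2.1.2 covers all azacitidine-treated TP53-mutant patients, so it does not show that non-responders progress soonest.

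**Conclusion.** The point holds in a limited form. After the end-of-treatment visit, later progression in non-responders who stop without PD and without new therapy is not systematically captured. The same responder-only wording in three places suggests a deliberate rule, one that serves duration of response better than PFS.

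The effect is modest. In the illustration about 2-5 of 33 patients have unseen progression, and the cohort shifts are small beside the 2.9-5.8 months by which an affected patient's own PFS is overstated on average. The size rests entirely on assumed inputs: the 4-month median, the share and timing of stopping, survival after progression, and stopping unrelated to prognosis. The actual share is not in the documents, and the larger reading of it in Step 3 gives a somewhat larger shift. This is a worthwhile, cheap improvement and does not threaten the trial's primary conclusions.

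**What to change.** In the synopsis follow-up text, footnote s of Table 8 and 7.4:

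1. Extend the monthly off-treatment assessment to *all patients who discontinue study treatment without relapse or PD*. Use blood counts and blasts, plus any local progression or marrow result obtained through the existing monthly contact or record review. Record the progression date.
2. For the added non-responders, continue until PD, death, withdrawal of consent or start of new anticancer therapy.
3. Leave the responders' follow-up as it is. Section 8.2.5 follows SCT recipients for relapse, and a stop at new therapy must not shorten that.
4. State that marrow-only progression off treatment may still be missed. Appendix I defines PD largely by marrow blasts, and its peripheral route needs a rise of more than 50% to above 25 × 10⁹/L.
5. Add to 9.5 a PFS sensitivity analysis for non-responders who stop without PD, for example dating the event at the last evaluable assessment instead of at death, and report how many patients are affected.

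Cost: a wording change in three places, one analysis, and a small site workload for a few patients, since monthly contact already exists. Capture of marrow progression remains incomplete.

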8.0 STUDY ASSESSMENTS

8.1 Safety Assessments

8.1.1 Safety Analysis

Safety data will be tabulated for all patients and include vital signs, laboratory parameters, and AEs.

8.1.2 Reporting of Adverse Events

8.1.2.1 Adverse Events

An AE is any untoward medical occurrence in a patient or clinical investigation subject administered a pharmaceutical product that does not necessarily have a causal relationship with the treatment. An AE can be any unfavorable and unintended sign (including a laboratory finding), symptom or disease temporally associated with the use of a medicinal (investigational) product, whether or not related to the medicinal (investigational) product.

The treatment-emergent AE reporting period starts at study treatment initiation. All treatment-emergent AEs will be collected for up to 30 days after the last dose of study treatment. At each evaluation, patients should be interviewed in a non-directed manner to elicit potential adverse reactions from the patient. The occurrence of an AE will be based on changes in the patient's physical examination, laboratory results, and/or signs and symptoms.

On Cycle 1, Day 1, any events observed from the time of signing informed consent but prior to initial study drug administration will be recorded as a serious or non-serious adverse event, if considered by the Investigator to be causally related to a study-required procedure or activity that was conducted prior to Cycle 1, Day 1 (i.e., screening period). Events observed from the time of signing informed consent, but prior to initial study drug administration that are not considered to be causally related to a study-required procedure or activity should be recorded on the medical history CRF page.

All AEs (except Grade 1 and 2 laboratory abnormalities that do not require an intervention), regardless of causal relationship, are to be recorded in the CRF and source documentation. The Investigator must determine the intensity of any AEs according to the NCI Common Terminology Criteria for Adverse Events (CTCAE) version 5.0 and their causal relationship. Those AEs not covered by these criteria will be graded as follows:

1. Mild: Discomfort noticed, but no disruption of normal daily activity. Prescription drug not ordinarily needed for relief of symptom but may be given because of personality of patient.
2. Moderate: Discomfort sufficient to reduce or affect normal daily activity. Patient is able to continue in study; treatment for symptom may be needed.
3. Severe: Incapacitating, severe discomfort with inability to work or to perform normal daily activity. Severity may cause cessation of treatment with test drug; treatment for symptom may be given and/or patient hospitalized.
4. Life-Threatening: Symptom(s) place the patient at immediate risk of death from the reaction as it occurred; it does not include a reaction that, had it occurred in a more serious form, might have caused death.
5. Fatal: Event caused the death of the patient.

AEs will be followed until resolution or stabilization while the patient remains on-study. Once the patient is removed from study, events thought to be related to the study medication will be followed until resolution or stabilization, unless, in the Investigator's opinion the event is unlikely to resolve due to the patient's underlying disease, or until the patient starts a new treatment regimen or the patient is lost to follow-up.

